Techniques for nasal swabs for evaluating of rapidly progressive dementia in prion diseases have been published previously. Indeed, for prion diseases, olfactory mucosal brushings or swabs provide a very high sensitivity and specificity of diagnosis (13). Previous evaluation of the nasal epithelium have shown increased levels of A-beta and p-tau in AD compared to controls, and a correlation between A-beta plaque frequency and p-tau in olfactory epithelium and brain in post-mortem examinations (although the correlation coefficient was 0.37) (14).

In spite of the low risk, relative simplicity of sampling, and the ability to test for characteristic pathological changes on CNS tissue directly, thus far, nasal mucosal swab or cytobrush techniques have not been used broadly for diagnosis of degenerative dementias (except for rapidly progressive dementias).

We propose this pilot study for evaluation of olfactory and vocal cord function, and nasal mucosal swabs of patient volunteers with neurodegenerative disorders or at risk of neurodegenerative disorders (identified as either having changes of presbylarynx on examination of laryngeal function, or with single or multi-domain mild cognitive impairment (MCI)) on standard neuropsychometric evaluations at the Psychiatric Research Institute for evaluation of cognitive symptoms. Neuropsychometric evaluations and cranial imaging (with or without olfactory evaluation) form the existing standard of care for patients considered at risk for neurodegenerative disorders.

We will obtain buccal and nasal mucosal swabs which will be used for standard immunohistochemistry (IHC) evaluations for neuronal, disease-specific and inflammatory markers. We will correlate olfactory dysfunction (measured by the University of Pennsylvania Smell Identification Test (UPSIT), performance on neuropsychometric testing including evaluation of anxiety and depression and quality of life measures, and cranial imaging results with the nasal mucosal cells obtained through swabs. We will also evaluate the functioning of the vocal folds during voice production (phonation) and closure of vocal folds, as well as any structural abnormalities in the vocal folds, hypopharynx, pharynx (throat) and larynx (voice box), as well as measuring the quality of sound produced, including breath control during speech, intelligibility of voice and its pitch and loudness through specific speech measures.

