Title: Smell, voice and nasal swabs as markers for neurodegenerative disorders
PI: [name]. MSPH; [name]
Site: University of Arkansas for Medical Sciences

Specific Aims

The specific aims of the study are:

- Aim 1: Determine if smell, voice or vocal cord dysfunction serves as a reliable markers to distinguish between neurodegenerative disorders or among subjects with and those without neurodegenerative disorders.
- Aim 2: Determine if nasal swabs can provide an adequate sample for evaluation using cytology and immunohistochemistry for alpha-synuclein, A-beta and p-tau staining.
- Aim 3: Measure cellular levels of IL-1 a/b protein and mRNA levels and genotyping of apo-E4 alleles on the nasal mucosal swab samples.
- Aim 4: Evaluate if IHC and neuro-inflammatory marker levels correlate with severity of impairment in various cognitive or motor domains based on neuropsychological and motor scores, or olfactory impairment based on UPSIT scores.

Study Population

This is a prospective cross-sectional study of subjects with, or at risk of neurodegenerative disorders. Initial recruitment goal is for 60 subjects:

- Twenty people with Parkinson's Disease requiring evaluation of voice dysfunction by an Ear, Nose, and Throat (ENT) doctor
- Twenty people with other neurodegenerative disorders requiring evaluation of voice dysfunction by an ENT doctor.
- Twenty people with voice tremor and/or presbylarynx, but no evidence of Parkinson's other neurodegenerative disease, requiring evaluation of voice dysfunction by an ENT doctor.

Subjects will be recruited from the population of patients with neurodegenerative disorders (seen in the UAMS Neurology Clinic) or presbylarynx and/or voice tremor patients scheduled to undergo routine voice and laryngeal assessments as part of required clinical care for problems with voice and swallowing in the UAMS ENT Clinic.

Inclusion Criteria

- Diagnosed with idiopathic Parkinson's disease, progressive supranuclear palsy, Alzheimer's disease or Mild Cognitive Impairment based on consensus criteria, or suspicion of presbylarynx based on clinical evaluation.
- Require evaluation of voice dysfunction by an ENT doctor given symptoms of impaired voice volume or quality

Title: Smell, voice and nasal swabs as markers for neurodegenerative disorders

PI: [name]. MSPH; [name]

Site: University of Arkansas for Medical Sciences

- Age \geq 18 years-old to \leq 90-years old.

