PI: [name]. MSPH; [name]
Site: University of Arkansas for Medical Sciences

authorized representative will be required for continued study participation. Since subjects with voice tremor and presbylarynx are expected to be cognitively normal, for this comparison group, neurological examination and MoCA can be performed after their ENT and speech therapy assessments (see below).

Demographics

Routine demographics, e.g., age, gender, race, ethnicity, will be collected.

Medical History

A routine medical and surgical history will be collected with a recent history of infections or nose and/or throat-related problems. Previous and concomitant medications will also be reviewed and recorded.

Review Eligibility Criteria

Documentation of subjects having an established diagnosis of Parkinson's Disease, other neurodegenerative disorders, or a voice tremor or presbylarynx will be reviewed at the time of screening.

In order to stratify subjects with appropriate diagnostic certainty of the underlying diagnosis of neurodegenerative disorder, subjects will undergo comprehensive neurological assessments (described under the study procedures section below) and review of previous assessments to ensure that they meet the current consensus criteria for neurodegenerative disorders (e.g., United Kingdom Parkinson Disease Brain Bank Diagnostic Criteria for Parkinson Disease, NINCDS-ADRDA diagnostic criteria for Alzheimer's Disease) after screening is completed.

This review will be done during the study-related neurological assessments, and will include review of imaging, neuropsychological data (if available), neurological history and examination performed during their study-related visit with the neurologist.

Study Procedures

Logistically, this study involves a routine otolaryngology clinic visit and a research-related neurology visit that are likely to occur over separate days. The research-related neurology visit and consent will take place in a dedicated research space at Translational Research Institute (TRI). The study visits will occur within 1 year of the providing informed consent, otherwise the subject will be deemed lost to follow up.

Otolaryngology Elements

Physical Exam (routine clinical care)

A general physical examination will be performed as part of routine care.

Title: Smell, voice and nasal swabs as markers for neurodegenerative disorders
PI: [name]. MSPH; [name]
Site: University of Arkansas for Medical Sciences

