We will use the smell identification Test [UPSIT] for evaluation of smell sensation. UPSIT is a 40 item test of smell function with established age based normative data. The test is a simple scratch and sniff test which comprises of four booklets each containing 10 micro-encapsulated odors printed onto a section of the page. Forced-choice responses accompany test item on the same page of the booklet as the scratch and sniff component. The test will be administered by the patient's under guidance of the investigator or coordinator. It usually takes about 10 to 15 minutes to self-administer the test. To evaluate if there is asymmetry of smell identification when using left and right nostril, a subset of participants will be administered the test twice, at the beginning and then at the end of their physical and neurological exam, and instructed to use one and then the other nostril while occluding the opposite nostril with their finger when inhaling. The smell test will take place in a dedicated research space at Translational Research Institute (TRI).

Buccal Swabs (only for research purposes)

Sample Collection. Oral mucosa samples from subjects will be obtained using two cotton swabs, and a board certified physician ([name]) will obtain the swabs by

Title: Smell, voice and nasal swabs as markers for neurodegenerative disorders
PI: [name]. MSPH; [name]
Site: University of Arkansas for Medical Sciences

scraping the inside of the cheek of the subject firmly with the swab, with the swab being placed in saline solution in two test tubes labeled with subject ID.

Nasal Swabs (only for research purposes)

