A comprehensive neurological history and neurological examination, Unified Parkinson's Disease Rating Scale (UPDRS), Schwab and England Activities of Daily Living scale, and the Montreal Cognitive Assessment (MoCA) as well as depression and anxiety scales (Hospital Anxiety and Depression Scale), quality of life scales (EQ-5D and Vision Function Questionnaire) as well as freezing of gait questionnaire (FOG-Q), will be performed by the neurologist for ensuring appropriate stratification based on the consensus criteria for various neurodegenerative disorders, or to ensure that subjects do not have incidental findings concerning for neurodegenerative disorders (if they are

Title: Smell, voice and nasal swabs as markers for neurodegenerative disorders
PI: [name]. MSPH; [name]
Site: University of Arkansas for Medical Sciences

being recruited to the voice tremor/presbylarynx group). If there are any concerns for neurodegenerative disorders based on examination, the neurologist completing the examination will discuss this with the subject and may provide a referral for clinical assessment.

Any prior neuropsychological evaluation results and imaging results (including those of functional imaging studies like Dopamine Transporter imaging (DATScan®) or PET Scans will be abstracted from the subjects' medical records as part of the study procedures during the subjects' neurology visits.

Gaze Tracking While Reading (only for research purposes)

We will use infrared oculography at 150- Hz to assess eye movements while the subject read aloud an English reading passages (Arial 36 point font, 5-8 words per line, 3-8 lines per page, 8 pages total) at 8th grade reading level, which will be displayed on a desktop computer monitor.

Risks and Benefits

Risks associated with the research-related procedures include significant time burden associated with participation, with the neurological examination, smell identification test, and OM sampling which in total are expected to take 4 hours of subject's time.

There is risk of discomfort and irritation of the nose associated with sampling of the OM. A potential risk to study participants exists in the potential for loss of confidentiality. Measures to protect the confidentiality of study participants will be implemented as described in the Data Handling and Recordkeeping section below.

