De-identified OM samples and linked accompanying study data (including diagnostic certainty, motor and cognitive scores as well as smell testing data from study related procedures) will be stored for future research, and may be shared, de-identified, with other researchers at or outside UAMS, provided the subjects have given their written informed consent. Regarding the genotyping of apo-E4, results will not be shared with the study subjects. There exist several uncertainties about the reliability of the small sample and we do not intend to validate the results against a traditional method since this is a proof of concept pilot study.

Subjects can withdraw their consent and require destruction of their samples/data to prevent their use in future research by sending a written request to Drs. [name] or [name].

Data Analysis

As a first pass, frequency distributions and cross tabulations will be obtained to look at the data. Counts of missing data will be obtained. The distributions will be looked at for heaping, skewness and general amenability to analysis. We will compare the individuals with Parkinson's disease to those with presbylarynx or other degenerative disorders to look for any demographic differences. Cross tabulations will be done between "independent" (diagnosis of Parkinson's disease versus presbylarynx or other degenerative disorders) and "dependent" variables including abnormalities on laryngoscopy or stroboscopy, performance on smell identification test as both a continuous measure, and when classified into hyposmia and anosmia based on age and gender expected norms.

Title: Smell, voice and nasal swabs as markers for neurodegenerative disorders
PI: [name]. MSPH; [name]
Site: University of Arkansas for Medical Sciences

Additionally, we will look at the presence of histopathological markers for inflammation and misfolded protein deposition by potential confounding variables like age, gender, duration of disease, treatment characteristics at baseline and performance on smell testing etc. If needed, analyses will be repeated using stratification to investigate the effect modification by age, gender and time since diagnosis of Parkinson Disease, etc. Since these are preliminary analyses to determine effect size estimates to help power future studies, a power sizes cannot be estimated at this time.

Ethical Considerations

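### Nothing in the protocol keeps the smell, laryngeal and speech results from the neurologist who confirms each subject's diagnostic group

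*Protocol*

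**What the plan says.** - **Aim (Specific Aims).** Aim 1 is to "Determine if smell, voice or vocal cord dysfunction serves as a reliable markers to distinguish between neurodegenerative disorders", or subjects with such disorders from those without.
- **Analysis (Data Analysis).** The independent variable is "diagnosis of Parkinson's disease versus presbylarynx or other degenerative disorders". The dependent side is "variables including abnormalities on laryngoscopy or stroboscopy, performance on smell identification test as both a continuous measure", and smell is also analysed in categories.
- **Entry (Inclusion Criteria; Review Eligibility Criteria).** Documentation of the diagnosis is reviewed at screening.
- **Confirmation (Review Eligibility Criteria).** After screening, the neurologist verifies that consensus criteria are met: "This review will be done during the study-related neurological assessments". The listed inputs are scans, any earlier neuropsychology, and the neurologist's own history and examination. Neurological Evaluation adds motor, cognitive, mood and quality-of-life scales.
- **Comparison group (Neurological Evaluation).** The same examination serves "to ensure that subjects do not have incidental findings concerning for neurodegenerative disorders".
- **Smell test (Smell Testing).** "The test will be administered by the patient's under guidance of the investigator or coordinator". A subset takes it twice, once before and once after the physical and neurological examination, using one nostril each time.
- **Order (Informed Consent).** For subjects with neurodegenerative disorders the neurological examination precedes laryngoscopy, stroboscopy and olfactory sampling. For the voice tremor and presbylarynx group, "neurological examination and MoCA can be performed after their ENT and speech therapy assessments".

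**The concern.** In Aim 1 the diagnostic group is the reference standard, and smell, voice and laryngeal findings are the index tests. If the person confirming the reference already knows an index result, the two are no longer independent. A low smell score could raise the recorded certainty of a borderline case, or prompt doubt about a comparison subject. Either would strengthen the association between marker and group.

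According to Data Analysis, the study exists to supply effect sizes for powering later studies. An inflated effect size carried into that planning would leave the next study too small. No later analysis can undo a diagnosis made with knowledge of the marker, so the safeguard belongs in the conduct of the visit.

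**Working it through.** The protocol gives no accuracy figure, power or effect size to reproduce. The check is therefore to trace who sets the group, when, and what could be known by then.

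**1. Who decides.** The neurologist, at the research neurology visit, for all three groups (Review Eligibility Criteria; Neurological Evaluation).

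**2. What could be known at that moment.**

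| Subjects | UPSIT relative to the neurological examination | Study ENT and speech results relative to it |
|---|---|---|
| Two-nostril subset | First test before, second after | As for the subject's group, below |
| All others | Not stated | As for the subject's group, below |
| Neurodegenerative groups (20 + 20 = 40 of 60) | As above | Examination precedes laryngoscopy and stroboscopy; speech assessment not mentioned in that rule |
| Comparison group (20 of 60) | As above | Examination may follow both |

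For subjects outside the subset, the only clue to UPSIT timing is the place. Smell Testing and Study Procedures put the test and the neurology visit in the same research unit, yet the test is listed under Otolaryngology Elements. The clue is suggestive, not decisive.

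**3. What separates the two.** Nothing is stated. No sentence blinds the neurologist to UPSIT, laryngoscopy or speech results, and none locks the group before they are known. The UPSIT may be guided by an investigator, and the diagnosing neurologist is not excluded.

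**4. Asymmetry.** Possible exposure to study laryngeal findings is open for the comparison group and closed by order for the other two.

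**5. How sensitive a group of 20 would be (illustration only).** The protocol gives none of these counts. Assume 6 of 20 comparison subjects are hyposmic, and that k of those 6 leave the group because the smell result was known. Apparent specificity = 14/(20 − k):

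- k = 0: 14/20 = 70.0%
- k = 1: 14/19 = 73.7%
- k = 2: 14/18 = 77.8%
- k = 3: 14/17 = 82.4%

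This shows only that a few reclassifications would be visible at this sample size. It does not estimate how many would occur.

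**The case against.** **The diagnosis predates the study test.** Subjects arrive with a documented diagnosis, so the visit mostly confirms it. This stands. It is wrong to infer that the group is first fixed at the visit where the smell test is given. It limits the risk without removing it, because some entry labels are soft (mild cognitive impairment, suspected presbylarynx) and the visit is meant to grade certainty.

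**The listed diagnostic inputs include no index test.** This also stands: the protocol permits contamination by silence and does not prescribe it. The Background remark that "Neuropsychometric evaluations and cranial imaging (with or without olfactory evaluation) form the existing standard of care" might suggest that the neurologist will use the smell result. It describes usual care for at-risk patients and makes olfaction optional, so it does not show that.

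**UPSIT timing is explicit only for the subset.** Correct. Even there, the first test uses one nostril, and nothing says it is scored before the examination ends.

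**The order already protects two of the three groups from laryngoscopy findings.** Correct; the ENT route concerns the comparison group alone. Those subjects are recruited for a laryngeal or voice condition, so much of that information is known anyway, and any neurologist hears the subject speak.

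**The Background error rates.** The 16% of expert-diagnosed Parkinson's disease without a dopamine transporter deficit and the 12.5% of Alzheimer's diagnoses with non-Alzheimer pathology may tempt a reader to size the problem. They show that clinical labels can be wrong. They do not show marker results influencing labels, and they say nothing about comparison subjects.

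**This is a descriptive pilot.** That lowers the stakes, but its stated product is effect sizes, which is what this path would distort.

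**Conclusion.** The concern holds in a limited form. The neurologist confirms group and certainty with no rule keeping the Aim 1 markers out of that decision. The path is explicit for smell in the two-nostril subset and for laryngeal and speech findings in the comparison group; for smell in other subjects it is merely not excluded. Any bias would most likely make smell look more discriminating, and laryngeal and voice findings to a lesser degree.

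The size cannot be derived from the protocol. The figures from 70.0% to 82.4% rest wholly on assumed counts, and Neurological Evaluation states no rule for moving a subject between groups, only discussion and possible referral. The conclusion assumes that a neurologist who sees a result may be influenced by it. It does not assume that this will happen. The change is worth making because it costs little and must be in place before data are collected.

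**What to change.** Add to Review Eligibility Criteria and Smell Testing:

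1. The neurologist records diagnostic group and certainty on a dated form, using the inputs already listed in Review Eligibility Criteria and Neurological Evaluation. This is done before the UPSIT is scored and without the study laryngoscopy, stroboscopy or speech results.
2. The coordinator, whom the protocol already allows to do so, guides and scores the UPSIT; the diagnosing neurologist does not. In the two-nostril subset the first booklet stays unscored until the form is signed.
3. The primary Aim 1 contrasts use the recorded group. Later changes of diagnosis are logged with their reason and shown in a sensitivity analysis. A rule that forbade any regrouping would go too far: it could keep in the comparison group someone who no longer meets its definition in Study Population, which requires no evidence of neurodegenerative disease.

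**Cost.** A few sentences and one form, with no added visit. UPSIT guidance would fall to the coordinator alone. The neurologist works without the UPSIT and the study ENT and speech results until the form is signed; the referral provision is untouched. Voice cannot be fully masked, because the neurologist hears the subject speak, so the protection is strongest for smell.

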The inability to establish a diagnosis is even more relevant in early stages of the disease, when specificity of establishing a diagnosis using the clinical diagnostic criteria is lower. As evidence, 16% of patients identified by PD experts as having PD for a longitudinal cohort study funded by the Michael J Fox Foundation for development of biomarkers for PD did not have a deficit in dopamine transporter (DAT) binding, suggesting that they did not indeed have PD (5). Similarly, in a large neuropathology study of patients diagnosed with mild to moderate AD at AD centers funded by the National Institute for Aging, 12.5% met neuropathological criteria for non-AD dementias (6). There is a clear need to develop diagnostic markers, yet blood, peripheral tissue and CSF markers have all lacked specificity to be of practical use in the clinic.

A common, early marker of several degenerative dementias is impaired smell sensation and changes in voice. Indeed, olfactory impairment has been reported in PD (7), FTLD (8), and AD (9). Voice changes appear early in many parkinsonian disorders (10), and language changes have been assessed as a marker of disease progression in

Title: Smell, voice and nasal swabs as markers for neurodegenerative disorders
PI: [name]. MSPH; [name]
Site: University of Arkansas for Medical Sciences

Alzheimer's Disease (11). Pathological involvement of the olfactory bulb has also been demonstrated with disease specific pathological changes (12). These changes are hypothesized to appear early in the pathological process, and olfactory neurons provide us a unique opportunity to evaluate disease specific pathological changes representative of dysfunction within the CNS in a non-invasive fashion, since these can be sampled using simple nasal brushings or swabs. Voice changes appear early in may parkinsonian disorders, and language changes have been assessed as a marker of disease progression in Alzheimer's Disease.

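### The one diagnostic grouping in the Data Analysis sets Parkinson's disease against everyone else, so Aim 1's comparison of subjects with and without neurodegenerative disease is specified for Parkinson's disease at most

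*Protocol*

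**What the plan says.** **Aim.** In Specific Aims, Aim 1 is to find out whether smell, voice or vocal cord dysfunction can "distinguish between neurodegenerative disorders or among subjects with and those without neurodegenerative disorders".

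**Groups.** Under Study Population, "Initial recruitment goal is for 60 subjects", in three sets of 20: PD, other neurodegenerative disorders, and "Twenty people with voice tremor and/or presbylarynx, but no evidence of Parkinson's other neurodegenerative disease". The Informed Consent section gives the third set its role: "Since subjects with voice tremor and presbylarynx are expected to be cognitively normal, for this comparison group", the neurological examination may follow the ENT and speech visits. The Neurological Evaluation section has a neurologist check that these subjects show no signs of neurodegenerative disease.

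**Analysis.** The Data Analysis section uses one diagnostic grouping twice. For baseline characteristics: "We will compare the individuals with Parkinson's disease to those with presbylarynx or other degenerative disorders to look for any demographic differences". For the outcomes (laryngoscopy or stroboscopy abnormalities and smell test results), the independent variable is "diagnosis of Parkinson's disease versus presbylarynx or other degenerative disorders". The remaining analyses are by age, gender, disease duration, treatment, smell performance and time since PD diagnosis; none adds a diagnostic contrast. The section describes these as "preliminary analyses to determine effect size estimates to help power future studies".

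**The concern.** The design takes care to build a disease-free comparator, and the analysis then does not use it as one. The grouping can be read in two ways, and neither delivers Aim 1.

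- **Pooled.** PD (20) is compared with the rest (40), half of whom have a neurodegenerative disorder and half of whom do not. The result is neither disease against disease nor disease against no disease. It is a mixture whose weights are set by the 20:20 recruitment split.
- **Two contrasts.** PD is compared with presbylarynx and, separately, with other disorders. The with-versus-without question is then answered for PD alone.

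Since effect sizes are the intended output, a contrast that is not planned is an estimate that the pilot does not plan to deliver. The label in the Data Analysis also leaves out voice tremor, although Study Population admits subjects with voice tremor alone to the third group.

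**Working it through.** **Recruitment total.** 20 + 20 + 20 = 60, as stated. The protocol gives no alpha, power or effect size to reproduce.

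**Contrasts Aim 1 calls for, against what each reading supplies**

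| Contrast | Pooled reading | Two-contrast reading |
|---|---|---|
| PD vs other disorders | no | yes |
| PD vs comparison group | no | yes |
| Other disorders vs comparison group | no | no |
| All neurodegenerative (40) vs comparison group (20) | no | no |

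The last two rows are empty on both readings. This is the main finding, and it needs no arithmetic.

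**Size of the distortion (smell only, pooled reading only).** Set the mean smell deficit to 0 in the comparison group, D in PD and kD in other disorders. The value of k is an assumption. The Background cites smell loss in PD, frontotemporal dementia and Alzheimer's disease, but gives nothing for progressive supranuclear palsy or mild cognitive impairment, both of which are eligible. I therefore show k from 0 to 1.

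- Pooled contrast: D − (20·kD + 20·0)/40 = (1 − k/2)D
- With versus without, 40 vs 20: (20·D + 20·kD)/40 − 0 = (1 + k)D/2
- Ratio of the two: (2 − k)/(1 + k), whatever D is

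The last two columns translate this into a later with-versus-without study: two-sample t test, two-sided 0.05, 80% power, D = 1 SD and within-group SD = 1 (all assumptions; the extra variance from mixing groups is ignored).

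| k | Pooled | With vs without | Ratio | n per group planned from pooled figure | n per group needed |
|---|---|---|---|---|---|
| 0 | 1.00 D | 0.50 D | 2.0 | 17 | 64 |
| 0.25 | 0.875 D | 0.625 D | 1.4 | 22 | 42 |
| 0.5 | 0.75 D | 0.75 D | 1.0 | 29 | 29 |
| 0.75 | 0.625 D | 0.875 D | 0.71 | 42 | 22 |
| 1 | 0.50 D | 1.00 D | 0.5 | 64 | 17 |

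The two agree only at k = 0.5. Below that the pooled figure overstates the with-versus-without effect; above it, it understates it.

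I make no such calculation for laryngoscopy or stroboscopy. All three groups are selected for voice dysfunction, so the direction of any distortion there is unknown. The missing contrasts apply to those outcomes all the same.

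**The case against.** The best counter-argument is that pooling is never stated. Every other section treats the three groups separately, so the phrase may be a loose list of three categories. A three-column cross tabulation would let a reader work out every contrast. On that view the rest is an omission of the kind a statistical analysis plan commonly fills, in a section that calls itself a first pass and contains no test or decision rule. The sample-size illustration also supposes that someone would size a with-versus-without study from a PD-versus-rest estimate, which the protocol does not say.

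Part of this stands. The distortion figures depend on the pooled reading and on assumed k and D, and have no fixed direction. The sample sizes show a possible misuse, not a planned step. No data are lost, because diagnosis is recorded for each subject. The voice-tremor label may be mere shorthand.

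The main point survives. A three-way list strains the word versus, and the demographic sentence plainly compares PD with the rest. This is also more than detail left for later: the protocol states a grouping, and that grouping does not match its own aim or its three-group design. The table of contrasts has the same two gaps on either of the two readings set out there.

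**Conclusion.** The point holds and should be fixed. As written, the analysis addresses Aim 1's with-versus-without question for PD at most, and not at all if the comparator is pooled. That conclusion follows from the text and rests on no assumption.

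The size is conditional. On the pooled reading, for smell, the planned estimate lies between half and twice the with-versus-without effect, for k between 0 and 1. The consequence is moderate: this is a pilot and the missing contrasts can be recovered from the data. But effect sizes are its stated product, and part of what Aim 1 asks for has no planned estimate.

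**What to change.** Define diagnosis as the three recruited groups (PD; other neurodegenerative; voice tremor and/or presbylarynx) and give each its own column in every cross tabulation, demographics included. Replace the current grouping with four named contrasts:

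1. all neurodegenerative (40) vs voice tremor/presbylarynx (20);
2. PD vs other neurodegenerative (20 vs 20);
3. PD vs voice tremor/presbylarynx (20 vs 20);
4. other neurodegenerative vs voice tremor/presbylarynx (20 vs 20).

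Report each as an effect size with a 95% confidence interval. Contrast 1 is itself a 20:20 mixture of PD and other disorders, so it should be read beside contrasts 3 and 4. The four are not independent, since three group means carry only two independent differences; they are named for clarity.

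**Cost.** One paragraph of protocol wording, with no new subjects or measurements. The intervals will be wide. With within-group SD = 1, the half-width is 2.024 × √(1/20 + 1/20) = 0.64 SD for 20 vs 20, and 2.002 × √(1/40 + 1/20) = 0.55 SD for 40 vs 20. The latter rises to 0.57 SD at k = 0 and D = 1 SD, when the spread between PD and other disorders is counted: the variance of the 40 becomes 1 + 0.25 = 1.25, and 2.002 × √(1.25/40 + 1/20) = 0.57.
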